TXA is a synthetic anti-fibrinolytic agent that competitively inhibits the activation of plasminogen to plasmin by blocking tissue plasminogen activator and at higher concentrations directly inhibits plasmin[4, 9]. Plasmin, an enzyme that degrades fibrin clots, fibrinogen, procoagulant factors V and VIII[4]. Inhibition of plasmin decreases proteolytic action thus leading to clot formation and stabilization[4]. TXA is indicated in patients with hemophilia for short-term use (two to eight days) to reduce or prevent hemorrhage and reduce the need for replacement therapy during and following tooth extraction[13]. Administering TXA during the surgery will reduce the amount of plasmin in the system decreasing blood loss within and after the surgery. One gram of intravenous tranexamic acid (TXA) will be administrated before tourniquet inflation and before closure of the incision, as 1 g has been shown to be a safe amount with minimal side effects[16].TXA has already been shown to decrease perioperative bleeding in total knee arthroplasty and total hip arthroplasty, without increasing the risk of deep vein thrombosis[1, 2, 6, 8, 11, 15, 18].

This study is not being conducted under an IND number and will be conducted under IND exemption. This investigation is not intended to be reported to the FDA in support of a new

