Information to be recorded pre-operatively includes age, sex, height, weight, BMI, and American Society of Anesthesiology (ASA) classification. Intra-operative information will also be recorded, including operative time, and estimated blood loss. During the surgery, a suction device is utilized to remove excess blood from the surgical site and sucked into the suction drain and placed into a measuring cup. We will measure the perioperative blood loss by looking at the measuring cup and seeing how much blood is inside. The objective is to have the average blood loss of the cohort receiving TXA less than the cohort not receiving TXA. Knee swelling postoperatively will be measured using the swelling ratio. The swelling ratio is defined as the circumference of the operative limb divided by the circumference of the contralateral limb. Pain severity scores at rest will be assessed by use of a visual analog scale (VAS; 0 = no pain, 10 =worst pain imaginable) at 0.5, 1, 1.5, 2, 4, 6, 24, and 48 hours as well as 7 days after surgery. Percocet consumption will be recorded at 24 hours, 1 day, 2 days and 7 days after surgery. Incidence of TXA-related side effects (nausea/vomiting, itching, anxiety, increased thirst, rapid heartbeat) in the first 24 hours will be noted. Time to discharge from the post-anesthesia care unit (PACU) and time to discharge from the hospital will be recorded. Patients will be in the study a duration of two weeks, until their post-operative follow up visit.

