## **Data and Safety Monitoring Plan**

Data monitoring will be done by [name], the anesthesiologist, and [name], the principal investigator will oversee the conduct of the study. They will review the following accumulated data quarterly.

They will monitor whether or not:

- 1. Collection and storage of patient data was performed in a sensitive and secure manner, as defined in the informed consent form and protocol, ensuring information is stored on REDCap.
- 2. All study activities were conducted with primary emphasis on patient care and wellbeing, ensuring the patients are not in discomfort and have an abnormally high VAS following the surgery.
- 3. If there were any adverse events, and if so were addressed appropriately and per protocol
- 4. The risk/benefit to patients has remained the same throughout the course of the study.

The study will be stopped if there are unexpected severe AE's in more than one patient. Adverse events will be defined as negative reactions to the intravenous TXA during or after surgery, including seizures, vision problems. We will submit summaries of data and safety monitoring annually.

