#### Adverse Event Reporting

Information about any breach of confidentiality will be documented in the electronic data collection system and/or on the paper CRFs, as appropriate. It will be the responsibility of the Principal Investigator to report any Serious Adverse Event (SAE) that occurs during the course

Version 2/26/20

of the prospective data collection to the Institutional Review Board (IRB) within the timeframe specified by NYU SoM.

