## Protection against Risks

Patients will be screened for any contraindication to aspirin or Percocet use.

The patients will stay in the recovery unit a minimum of 3 hours after surgery as the mean duration of the effect of TXA is 3 hours and be monitored by the recovery unit nurses[3, 12]. Patients will be instructed to call the principal investigator and visit the emergency department if there is are any symptoms of calf swelling or chest pain within the first seven days following surgery.

Additionally, all patients will be de-identified and given a code. Information linking the patient codes to the participants' names and medical record numbers will be stored in a secure location separate from the medical information. Access to the information linking the linkage codes with participant identifiers shall be restricted.

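### The only planned side-effect outcome is five symptoms in the first 24 hours, and no rule yields a count by cohort of thromboembolic, seizure or vision events, so the hypothesis of few side effects relative to control cannot be properly supported

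*Combined protocol and SAP*

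**What the plan says.** All references are to the combined protocol and SAP.

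- **Hypothesis (section I, Rationale).** TXA is expected to reduce bleeding with few side effects relative to the cohort that does not receive it. The same section cites hip and knee arthroplasty literature reporting benefit "without increasing the risk of deep vein thrombosis".
- **Outcome (section III, Methods and Procedures).** "Incidence of TXA-related side effects (nausea/vomiting, itching, anxiety, increased thirst, rapid heartbeat) in the first 24 hours will be noted". Each patient is in the study for two weeks, until the follow-up visit.
- **Endpoints (Data Analysis and Statistical Plan).** Pain, blood loss and knee swelling. No safety endpoint is named.
- **Monitoring (Data and Safety Monitoring Plan).** "Adverse events will be defined as negative reactions to the intravenous TXA during or after surgery, including seizures, vision problems". The quarterly review asks "If there were any adverse events, and if so were addressed appropriately and per protocol", and there is a stopping rule: "The study will be stopped if there are unexpected severe AE's in more than one patient".
- **Serious events (Adverse Event Reporting).** The principal investigator must "report any Serious Adverse Event (SAE) that occurs during the course" of prospective data collection to the IRB.
- **Advice to patients (section IV, Protection against Risks).** Patients are to call the principal investigator and go to the emergency department for "symptoms of calf swelling or chest pain within the first seven days following surgery".
- **Risk list (section IV, Risk).** This includes chest pain, vision changes, limb pain or swelling, and breathlessness, with seizures among the rare effects.

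**The concern.** A comparative safety statement needs the same events to be sought, in the same way and over the same period, in both cohorts. Here the outcome that would support the statement is short in content and in time. It contains no thromboembolic, seizure or vision event and closes after the first day of a two-week follow-up. The provisions that do reach more serious events serve monitoring and reporting, and none says that events will be tabulated by cohort.

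At stake is what the trial report can say. A DVT on day 5 would not enter the side-effect outcome, so the report could describe side effects as few on the strength of five first-day symptoms. Events not asked about during follow-up are hard to recover reliably afterwards.

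**Working it through.** The documents give no safety event rate, margin or power, so there is no stated figure to reproduce. The check is mainly a comparison of the text, followed by arithmetic on what 55 patients per cohort (section II, Number of Subjects) could show.

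**Step 1. The provisions side by side**

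| Place | Events | Window | How they arise | Count by cohort |
|---|---|---|---|---|
| Methods and Procedures | Five symptoms | First 24 hours | Noted by the study | Possible, for these five only |
| Data and Safety Monitoring Plan | Reactions to TXA; seizures and vision problems named | During or after surgery, no end stated | Quarterly review; no schedule for asking | None stated; the wording cannot reach the no-TXA cohort |
| Adverse Event Reporting | Any serious adverse event | Prospective data collection | Report to the IRB | None stated |
| Protection against Risks | Calf swelling, chest pain | Seven days | Patient calls | None stated |

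The risk list in section IV has 16 items plus 5 rare ones, 21 in all. Four of them (nausea or vomiting, anxiety, thirst, fast heartbeat) are on the 24-hour checklist. The fifth checklist item, itching, is not on the risk list, so the two lists have not been reconciled. No section names DVT or PE as an event to record or schedules a question about it.

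**Step 2. Window**

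The checklist covers 1 day, against 7 days of symptom advice and about 14 days in the study. About 13 of 14 days lie outside it.

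**Step 3. Chance of at least one event among 55 TXA patients**

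Formula: 1 − (1 − p)^55. The rate p is assumed, because the documents give none.

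| Assumed p | Chance of at least one event |
|---|---|
| 0.1% | 5.4% |
| 0.5% | 24.1% |
| 1% | 42.5% |
| 2% | 67.1% |

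**Step 4. What zero events would exclude**

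The one-sided 95% upper bound for 0/55 is 1 − 0.05^(1/55) = 0.053, or 5.3%. The two-sided exact 95% interval has upper limit 1 − 0.025^(1/55) = 0.065, or 6.5%.

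**Step 5. What a test could detect**

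For k versus 0 events with 55 per cohort, the two-sided Fisher p-value is 2 × C(55,k)/C(110,k). It is 0.057 for k = 5 and 0.027 for k = 6, so 6 versus 0 events are needed for p<0.05. Even complete collection would support description, not a comparative test.

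**The case against.** A reader might infer that the trial does not capture serious harms at all. The documents do not support that. The monitoring plan names seizures and vision problems, reviews adverse events quarterly and requires annual summaries. Its definition is introduced by "including seizures, vision problems", which does not make the list exhaustive. Reporting of serious adverse events is limited neither to TXA reactions nor to 24 hours. A serious PE or seizure on day 4 therefore has a route into the records.

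A reader might also infer that the seven-day window applies to seizures and vision problems. It does not: it covers calf swelling and chest pain only. Nor is a favourable safety result close to guaranteed. Four of the five checklist symptoms come from the main risk list rather than the rare one, and they could differ between cohorts in either direction.

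Three further points have weight. The protocol gives the mean duration of TXA effect as 3 hours, so 24 hours is a reasonable window for transient symptoms. Safety is not a stated objective; it appears only in the hypothesis. The arthroplasty citation and the standard-of-care aspirin do not show that the plan regards DVT as a harm of TXA.

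These points narrow the issue without removing it. The monitoring definition cannot by its wording give a control count, IRB reporting is case by case, and the seven-day advice depends on the patient calling. The 3-hour duration explains the window for the five symptoms, but not the absence of any scheduled question about the events for which patients are told to seek care during the first week.

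**Conclusion.** The point holds as a gap in systematic, comparable collection. As written, the plan cannot properly support the statement about side effects relative to controls, because the only side-effect outcome is five symptoms in 24 hours and the broader provisions give no count by cohort. Thromboembolic events are the weakest spot, being named neither in the outcome nor in the adverse event definition.

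Its size cannot be expressed as a number of missed events. The step 3 probabilities run from 5.4% to 67.1% over assumed rates of 0.1% to 2%. They count any event, not only those that would fall outside the present rules, so quoting only the upper part of that range would overstate the case. The firm figures are the limits on what complete collection could show: an upper bound of 5.3% with 0/55, and 6 versus 0 events for significance. They assume that all 55 TXA patients (and, for the test, all 55 controls) are followed. The case for change is complete descriptive reporting, not a powered safety comparison.

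**What to change.** 1. In Methods and Procedures, keep the 24-hour symptom checklist. Add symptomatic DVT/PE, chest pain, seizure and vision disturbance, asked in the same words in both cohorts at the contacts already planned for pain and Percocet use (24 hours, 48 hours, day 7) and at the two-week follow-up visit.
2. In the Data Analysis and Statistical Plan, state that these events will be reported as counts by cohort with exact confidence intervals, as description only.
3. In the Data and Safety Monitoring Plan, reword the adverse event definition so that it applies to both cohorts and does not presuppose exposure to TXA.
4. Reconcile the checklist, the adverse event definition, the risk list and the seven-day advice. The stopping rule depends on the word unexpected, and the documents do not say whether events already on the risk list count as such. The sponsor should reconcile those passages too; no change to the rule itself is proposed here.

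The cost is a few extra questions at existing contacts, with no new visit or test. The report will have to show wide intervals for rare harms.

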#### **Data Analysis and Statistical Plan**

Statistical analysis will be performed using chi-squared and/or fisher's exact testing depending on size for binary variables. An a priori power analysis was conducted to estimate the minimum sample size needed to achieve 83% power (1 - b) at the .05 significance level which was calculated to be 50 patients. Therefore, we added 10 patients to account for potential exclusions, totaling 110 patients. Variables used in the power calculation were taken from the literature including an assumed effect size of 0.5 and standard deviation (SD) of 2. This large sample size will provide enough information to truly determine a difference between cohorts. This sample size and statistical analysis was used in similar studies looking at the effects of TXA in ACL

Version 2/26/20

reconstruction[5, 12].

Continuous variables will be compared with paired t-tests if the data is approximately normally distributed. If the data is not normally distributed, Mann-Whitney tests will be used. All protected health information will be removed prior to statistical analysis. We will use patient subjective pain, perioperative blood loss and knee swelling data as statistical endpoints. Subjective pain will be measured with the VAS (visual analogue scale), perioperative blood loss will be measured looking at blood loss from the suction drain after surgery. We are looking for a statistically significant difference in perioperative blood loss between the two cohorts. The swelling ratio is defined as the postoperative mean circumference of upper pole of patella and lower pole of patella divided by the preoperative values according to our previous study[9]. The endpoints must be statistically significant between the two cohorts to show TXA is effective.

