#### **Primary Objective**

The primary objective of the study is to determine if there are any differences in blood loss between patients undergoing BTB anterior cruciate ligament reconstruction who receive TXA compared to patients who do not receive it.

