#### **II. CHARACTERISTICS OF THE RESEARCH POPULATION**

#### Number of Subjects

We will aim to enroll a total of 110 subjects (55 per cohort) as determined by the priori sample size calculator.

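### The stated 83% power at 50 patients does not follow from the plan's own inputs: at d = 0.5, 50 per cohort gives 69.7% two-sided or 79.9% one-sided

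*Combined protocol and SAP*

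**What the plan says.** The Data Analysis and Statistical Plan reports the "sample size needed to achieve 83% power (1 - b) at the .05 significance level which was calculated to be 50 patients". Its inputs, said to come from the literature, are an "assumed effect size of 0.5 and standard deviation (SD) of 2". It continues: "Therefore, we added 10 patients to account for potential exclusions, totaling 110 patients".

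The Number of Subjects section traces a different per-cohort figure to the calculation: "We will aim to enroll a total of 110 subjects (55 per cohort) as determined by the priori sample size calculator".

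Sidedness is not stated. The Primary Objective is to "determine if there are any differences in blood loss between patients" with and without TXA, and the statistical section says "We are looking for a statistically significant difference in perioperative blood loss between the two cohorts". Both are non-directional. Methods and Procedures is directional: "The objective is to have the average blood loss of the cohort receiving TXA less than the cohort not receiving TXA". The hypothesis at the end of the Rationale also predicts a reduction in bleeding.

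On the test, the statistical section says "Continuous variables will be compared with paired t-tests if the data is approximately normally distributed", with Mann-Whitney otherwise. The power calculation itself names no endpoint, units, test or sidedness.

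**The concern.** A standardized effect of 0.5 with 50 per group is a familiar setting, and two-sided power there is known to be nearer 70% than 83%. An SD quoted beside an effect size is also odd: a standardized effect needs no SD, and a raw difference of 0.5 with SD 2 would be a standardized effect of only 0.25.

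This is the only justification given for the sample size, and the plan relies on it to say that the trial is large enough to settle the question. It also makes statistical significance the criterion for calling TXA effective. If the real power is lower, a non-significant result would be taken as stronger evidence against an effect than it is.

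**Working it through.** **Inputs**
- From the Data Analysis and Statistical Plan: power 83%, alpha .05, effect size 0.5, SD 2, minimum 50, plus 10, total 110.
- From Number of Subjects: 55 per cohort, 1:1.
- Inferred: 50 is per cohort, because 2 × 50 + 10 = 110, whereas 50 + 10 = 60.
- Assumed: two-sided, from the non-directional wording of the primary objective. One-sided results are shown beside it.
- Assumed: independent cohorts, because each patient is randomized to one cohort.

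**Formula.** For an independent two-sample t-test with n per cohort, the noncentrality is d × √(n/2) on 2n − 2 degrees of freedom. Power is the probability that the noncentral t exceeds the critical value.

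**Trying to reproduce 83% at 50 per cohort, d = 0.5**
- Noncentrality 0.5 × √25 = 2.50, on 98 degrees of freedom.
- Two-sided, critical value 1.984: power 69.7%, which is 13 points below 83%.
- One-sided, critical value 1.661: power 79.9%, which is 3 points below.
- The normal approximation gives 70.5% and 80.4%, so the method does not explain the gap.

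**Where 83% does appear**
- At 55 per cohort, d = 0.5: noncentrality 0.5 × √27.5 = 2.62, on 108 degrees of freedom. Two-sided 73.8%; one-sided 83.2%.
- Solving for 83% gives n = 54.7 per cohort one-sided and 68.9 two-sided. So 55 per cohort (110 evaluable) is needed one-sided and 69 per cohort (138 evaluable) two-sided.

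**Other readings**

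| Reading | Two-sided | One-sided |
|---|---|---|
| d = 0.5, 50 in total (25 per cohort) | 41.0% | 53.9% |
| d = 0.5/2 = 0.25, 50 per cohort | 23.6% | 34.3% |
| d = 0.25, 55 per cohort | 25.5% | 36.6% |
| Mann-Whitney, d = 0.5, 50 per cohort (efficiency 3/π) | 67.7% | 78.2% |

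Because the plan names a paired t-test, that was tried too. With 50 pairs, two-sided power is 93.4% at d = 0.5 and 41.0% at d = 0.25. A one-sided paired test on 110 pairs with difference 0.5 and SD 2 gives 83.2%, because 0.25 × √110 = 2.62 is the same noncentrality as above. Two separate cohorts of 55 contain no such pairs.

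No reading tried gives 83% at 50.

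**Risk of missing the assumed effect (d = 0.5).** The stated risk is 100 − 83 = 17%. Two-sided it is 100 − 69.7 = 30% at 50 per cohort and 100 − 73.8 = 26% at 55. One-sided it is 20% and 17%.

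**What the design can detect.** With 83% power two-sided, the detectable d is 0.59 at 50 per cohort and 0.56 at 55.

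**The case against.** The best defence is that the calculation was one-sided and returned 55 per cohort. Number of Subjects credits the calculator with 55, the hypothesis and Methods and Procedures are directional, and the figure then comes out at 83.2%. On that view the fault is a misdescription of the extra 10 patients, the shortfall at 50 per cohort is only 3 points, and the 26–30% miss rate falls to 17–20%.

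This may well be how the number arose, and the size of the gap does depend on sidedness. It does not rescue the text. No one-sided test is stated anywhere, the statistical section says that the calculation returned 50, and reaching 83% uses every patient said to be held in reserve for exclusions.

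A second objection is that the calculation never says which endpoint it powers, so attaching d = 0.5 to blood loss goes beyond the page. This stands in part. The power for a given standardized difference in blood loss is correct whatever the source of the 0.5, but only the sponsor can say whether 0.5 SD is a realistic blood-loss effect.

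It is also true that a wrong power statement neither biases the estimate nor inflates type I error, and that a confidence interval would show how informative a null result is. The statement is still the sole basis for the sample size.

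**Conclusion.** The stated power is wrong as written and must be corrected. With d = 0.5 and independent cohorts, 50 per cohort falls short of 83% by 13 points two-sided and by 3 points one-sided. That it falls short does not depend on sidedness; how far it falls short does.

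The result rests on reading 50 as per cohort and 0.5 as standardized. Both readings favour the plan, since taking 50 as a total or 0.5 as a raw difference with SD 2 lowers the power further. The 26–30% miss rate applies only if the test is two-sided. Confidence is high.

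**What to change.** Keep 110 patients and rewrite the sample-size paragraph along these lines:

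> Fifty evaluable patients per cohort (100), plus 10 for exclusions, gives 110. With a two-sided alpha of .05 and an independent two-sample comparison of blood loss, power is about 70% for a standardized difference of 0.5 (74% if all 55 per cohort are evaluable). Power is 83% for a standardized difference of about 0.59 (0.56 at 55 per cohort).

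The sponsor should also:
- give the blood-loss difference and SD in mL, with their source, that the standardized difference represents;
- remove or explain the SD of 2;
- if a one-sided .05 test was intended, say so and report about 80% at 50 and 83% at 55 per cohort;
- make Number of Subjects and the Data Analysis and Statistical Plan agree on whether the calculation returned 50 or 55 per cohort.

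The cost is protocol wording and a less favourable stated power, with no added patients. Holding 83% two-sided at d = 0.5 would instead need 138 evaluable patients, against 100 to 110 now. With the plan's own allowance of 10/110 = 9.1%, that is 69/(1 − 0.091) = 75.9, so 76 per cohort or 152 enrolled.

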#### Study Design

This will be a single-center, double-blinded randomized controlled study. The study is comparing blood loss and postoperative pain and swelling in two cohorts: patients undergoing BTB ACL reconstruction who receive TXA during surgery and patients who do not receive TXA. The intravenous tranexamic acid will be administered before surgery begins and after the tourniquet is released at the conclusion of the surgery. Blood loss will be measured via measuring the amount of blood in the drain at the conclusion of the surgery. Patients will be asked on postoperative day 1, 2 and 7 to rate their pain according to the VAS scale. Patients will have their knee swelling measured immediately postoperatively and at their one-week follow up visit. The swelling ratio is defined as the postoperative mean circumference of upper pole of patella and lower pole of patella divided by the preoperative values.[9]

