#### Version 2/26/20

medical histories will be performed based on their electronic medical records to identify any current pain medications or exclusion criteria. In order to maintain the blind, the resident assisting the surgeon will randomize the patient to one of two cohorts using REDCap. Both the resident and surgeon are members of the study team.

- Cohort 1: 1 gram of intravenous tranexamic acid (TXA) before tourniquet inflation and 1 gram of IV TXA before closure of the incision
- Cohort 2: Will not receive TXA.

The resident physician and anesthesiologist will not be blinded to the study, however the surgeon and study team members will remain blinded. Before the surgery begins, the resident will prepare the patient and the TXA will be administered (if assigned) before the tourniquet is placed, at which point the surgeon will be called into the room. The administration of TXA will not prolong the surgery and will not add any additional risks of prolonged anesthesia The surgeon will exit the surgery before closure at which point, the TXA will be administered (if assigned) and the resident physician will close the incision.

Immediate post-operative management will not be affected by this study. All patients will receive a standardized regimen of aspirin for DVT prophylaxis and Percocet for pain management, which is standard of care post-operative treatment.

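### The paired t-test named for approximately normal continuous endpoints, primary blood loss included, does not fit two independently randomized cohorts, because the design defines no pairs between them.

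*Combined protocol and SAP*

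**What the plan says.** The Data Analysis and Statistical Plan section has one rule for continuous variables, with two branches. For approximately normal data: "Continuous variables will be compared with paired t-tests if the data is approximately normally distributed". Otherwise: "If the data is not normally distributed, Mann-Whitney tests will be used". The same section lists pain, perioperative blood loss and knee swelling as endpoints, and the Primary Objective makes blood loss the primary one.

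The design is described elsewhere as follows.

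- Study Design: the two cohorts are "patients undergoing BTB ACL reconstruction who receive TXA during surgery and patients who do not receive TXA".
- Methods and Procedures: the resident will "randomize the patient to one of two cohorts using REDCap".
- Number of Subjects: 110 in total, 55 per cohort.
- Methods and Procedures, on blood loss: "The objective is to have the average blood loss of the cohort receiving TXA less than the cohort not receiving TXA".
- Data Analysis and Statistical Plan, on the contrast sought: "We are looking for a statistically significant difference in perioperative blood loss between the two cohorts".

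No section describes matching, crossover, bilateral surgery or allocation in pairs.

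**The concern.** A paired t-test analyses one difference per pair. Here the two values to be subtracted would come from different patients with no link between them, so the test has no defined input. An analyst who follows the text literally has to choose which TXA patient is set against which control. The plan gives no rule for that choice and does not say when it must be made.

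This is one of only two analyses available for the primary endpoint. Whether it is reached depends on a normality judgement, and the documents give no distribution for drain volume. If it is reached, the p-value depends on an arbitrary ordering, and patients are discarded when the cohorts differ in size. An analyst who quietly runs a different test instead departs from the written plan on the primary endpoint.

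**Working it through.** **Step 1: is there any pairing the test could use?** Blood loss is read once per operation from the measuring cup (Methods and Procedures), so it has no partner value. Some secondary measures do have within-patient pairs: pre- and postoperative circumference, operative and contralateral limb, repeated VAS. Those pairs do not compare TXA with no TXA, which is the contrast the plan requires.

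**Step 2: does the plan's sample size imply pairs?** Stated inputs: 83% power, significance level 0.05, effect size 0.5, SD 2, minimum 50, read as per cohort because 2 × 50 + 10 = 110. The 50 is not reproduced under either test (exact t calculations).

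- Independent two-sample test, standardized difference d = 0.5: 69 per cohort two-sided, 55 one-sided.
- Paired test, standardized within-pair difference 0.5: 36 pairs two-sided, 29 one-sided.
- If 0.5 is a raw difference, d = 0.5 / 2 = 0.25, and the independent test needs 273 per cohort two-sided.

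The enrolment target of 55 per cohort gives 83.2% power for an independent one-sided test at d = 0.5. So the sample size gives no sign of a paired design. Its failure to reproduce is a separate matter.

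**Step 3: what does an invented pairing do to the test?** With n pairs, t = D̄ / (s_D / √n) on n − 1 degrees of freedom, where s_D² = s_A² + s_B² − 2·s_AB. When the cohorts are equal, D̄ is the difference in cohort means whatever the pairing. The sample covariance s_AB, and hence the p-value, changes with every re-pairing. Degrees of freedom fall from 2n − 2 to n − 1.

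**Step 4: power, two-sided 0.05, normal data, noncentral t.** The noncentrality is d·√(n₁n₂/(n₁+n₂)) for the independent test and d·√(m/2) for m arbitrary pairs, with m the smaller cohort. At 50/50 and d = 0.5 both equal 2.5, so only the degrees of freedom differ (98 against 49).

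| Cohort sizes | d | Independent | Arbitrary pairs |
|---|---|---|---|
| 50 / 50 | 0.5 | 69.7% | 68.8% |
| 55 / 55 | 0.5 | 73.8% | 73.1% |
| 51 / 49 | 0.5 | 69.7% | 67.9% |
| 52 / 48 | 0.5 | 69.6% | 67.0% |
| 55 / 45 | 0.5 | 69.3% | 64.0% |
| 50 / 50 | 0.25 | 23.6% | 23.2% |
| 55 / 55 | 0.25 | 25.5% | 25.1% |

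**Step 5: how likely are unequal cohorts?** The plan itself allows for exclusions: "we added 10 patients to account for potential exclusions". As an illustration, if 10 of 110 are lost at random from 55/55, sizes stay equal in 25.8% of trials, differ by 4 or more in 32.0%, and reach 55/45 in about 0.12%.

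**Step 6: simulation, normal data, equal cohorts of 50 or 55, 8,000 trials per setting, 200 random pairings each.**

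- One pairing made blind to outcome: type I error 5.2% (50) and 5.1% (55), against 5.0% and 5.1% for Welch.
- One such pairing gives a different verdict from Welch in 3.4–4.0% of trials at d = 0.25 to 0.5, and in about 1.2% under the null.
- At least one of 200 pairings gives a different verdict in 23–26% of trials at d = 0.25 to 0.5.
- Taking the most favourable of 200 pairings: type I error about 12%. Smaller repeat runs gave about 11–12%.

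In one simulated data set (50 per cohort, SD 2, true difference 1), the independent test gave p = 0.015, while 5,000 pairings of the same data gave p from 0.0016 to 0.053.

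**The case against.** The strongest reply is that this is a slip of one word. Mann-Whitney is an independent-samples test, the plan speaks of a difference between cohorts, and an analyst with two unlinked columns would most likely run a two-sample test. Even a literal reading does little damage if the pairing is blind to outcome. The 11–12% error rate needs a deliberate search after the data are seen, the 55/45 split is very unlikely under random exclusions, and the branch is never reached if drain volume is judged non-normal.

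Most of this stands, and it limits the size of the problem. Intent probably was a two-sample test, typical harm is small, and the search and the 55/45 split are extremes. More ordinary splits such as 51/49 or 52/48 cost about 2 to 3 points of power at d = 0.5. None of it makes the written test correct. This section is the only analysis plan, its two branches assume different data structures, and no other text resolves the conflict.

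**Conclusion.** The concern holds. The named parametric test is wrong for the between-cohort comparisons, and for primary blood loss no pairing of any kind exists. This conclusion follows from the design and does not depend on the sample-size inputs.

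The size of the effect assumes normal data, a two-sided 0.05 test and a standardized difference of 0.25 to 0.5. That range is used because the plan does not say whether its 0.5 is standardized. On those terms a blind pairing of equal cohorts leaves error control intact and costs under 1 point of power. The cost grows when exclusions make the cohorts unequal. The main reason to correct it is that the plan leaves open a choice that can alter the primary p-value and can be made after the data are seen. It should be fixed before analysis, but it is not a threat to the trial as designed.

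**What to change.** In the Data Analysis and Statistical Plan section, replace paired t-tests with independent two-sample t-tests (for example Welch, which does not assume equal variances) for every between-cohort comparison of a continuous endpoint. Keep Mann-Whitney as the alternative for non-normal data. Reporting the mean difference with its 95% confidence interval is optional good practice. Make the change before the data are unblinded. The cost is one line of protocol wording, with no extra data or patients.
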